The sample size for this study is based on the event-driven analysis that is planned for comparing treatment groups within the high-risk stratum. For the purposes of this study, it is assumed that the placebo-treated non-Hispanic/Latino Caucasian subjects in the high-risk stratum will have an event rate of 15% over a 5-year period. This is more conservative than the 18% cited in the table, to assure adequate sample size. With an expected improvement of a reduction in event rate of 40%, the target event rate for the active treatment group will be 9% over 5 years. Furthermore, the following specifications are used: alpha=0.01, a 2-sided statistical test based on survival analysis, power=90%, annual dropout rate of 12% (or cumulative dropout rate of 47% over 5 years). In order to detect a difference of the specified magnitude ($\geq 40\%$ reduction in conversion rates over 5 years), at least 202 events must be observed during the course of the study in non-

Hispanic/Latino Caucasian subjects (primary analysis). Based on these assumptions and the fact that only non-Hispanic/Latino Caucasian subjects will be used for the primary analyses, a total of 2,346 non-Hispanic/Latino Caucasian subjects (1,173 on pioglitazone/1,173 on placebo) are required from the high-risk stratum for randomization.

Sample Size for the Phase 3 Study Based On Qualifying the Test Used to Stratify Subjects

While using data from the results of risk stratification and not a comparison between randomized groups, the same analysis as specified for comparing the treatment groups within the high-risk stratum will also be used to compare the two placebo groups (high-risk placebo and low-risk placebo). Thus, assuming that the placebo-treated subjects in the low-risk stratum will have a conversion rate of 4% over a 5-year follow-up period, then approximately 314 non-Hispanic/Latino Caucasian subjects identified as low-risk for the event are required in that stratum. While this number of subjects enrolled in the low-risk stratum will provide very high power (99% with $\alpha=0.01$) to validate the enrichment algorithm with the assumed 5-year conversion rates (ie, 15% vs. 4%).

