The sample size for this study is based on the event-driven analysis that is planned for comparing treatment groups within the high-risk stratum. For the purposes of this study, it is assumed that the placebo-treated non-Hispanic/Latino Caucasian subjects in the high-risk stratum will have an event rate of 15% over a 5-year period. This is more conservative than the 18% cited in the table, to assure adequate sample size. With a clinically meaningful improvement of a reduction in event rate of at least 40%, the target event rate for the active treatment group will be 9% over 5 years. Furthermore, the following specifications are used: $\alpha=0.01$, a 2-sided statistical test based on survival analysis, power=90%, annual dropout rate of 12% (or cumulative dropout rate of 47% over 5 years). In order to detect a difference of the specified magnitude ($\geq 40\%$ reduction in conversion rates over 5 years), at least 202 events must be observed during the course of the study in non-Hispanic/Latino Caucasian subjects (primary efficacy analysis). Based on these assumptions and the fact that only non-Hispanic/Latino Caucasian subjects will be used for the primary analyses, a total of 2,346 non-Hispanic/Latino Caucasian subjects (1,173 on pioglitazone/1,173 on placebo) should be enrolled from the high-risk stratum for randomization.

Sample Size for the Phase 3 Study Based On Qualifying the Test Used to Stratify Subjects

While using data from the results of risk stratification and not a comparison between randomized groups, the same analysis as specified for comparing the treatment groups within the high-risk stratum will also be used to compare the two placebo groups (high-risk placebo and low-risk placebo). Thus, assuming that the placebo-treated subjects in the low-risk stratum will have a conversion rate of 4% over a 5-year follow-up period, then approximately 314 non-Hispanic/Latino Caucasian subjects identified as low-risk for the event should be enrolled in that stratum. This number of subjects enrolled in the low-risk stratum will provide very high power (99% with $\alpha=0.01$) to validate the enrichment algorithm with the assumed 5-year conversion rates (ie, 15% vs. 4%).

Sample Size for the vMRI Substudy

This substudy is not designed or powered to assess any quantitative changes in the brain. Based on clinical judgment, a sample size of 300 subjects is believed to be sufficient to evaluate possible qualitative changes in the brain via vMRI.

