- For the hazard rate model, number of intervals for the piecewise constant baseline hazard function will be selected using $AIC_{Surv|Long}$ [Ref. 2]. Treatment effect on the hazard function will be evaluated by including treatment as a fixed factor. Other covariates (age, years of education, gender, and pooled center) included in the primary CPH model will also be included. Conditional power will be calculated using the value of the t statistic for testing the treatment effect on the hazard rate.

- Following subgroup analyses on the primary efficacy endpoint will be performed when there are at least 20% of the total primary efficacy events in the futility analysis in a subgroup:
 - Gender (male vs. female)
 - APOE risk-status (Low, High – where High denotes carriage of at least one APOE ε4 allele)
 - Baseline MMSE (≤ 27 vs. ≥ 28)
- Following subgroup summaries and MMRM analyses on the change from baseline in the composite score, CVLT-II Long and Short Delay Free Recall, BVMT-R Delayed Recall and MMSE total score will be performed when there are at least 400 subjects in a subgroup:
 - Gender (male vs. female)
 - APOE risk-status (Low, High – where High denotes carriage of at least one APOE ε4 allele)
 - Baseline MMSE (≤ 27 vs. ≥ 28)
- If the conditional power value is $>10\%$ but $<30\%$, “progression” of the conditional power in terms of an increasing number of the events vs. total needed will be provided for the following information fractions: 10% (20 events), 20% (41 events) and 34% (69 events) will be provided. The events will be selected based on the time of the occurrence of the event relative to the first dose. When the evidence against the null hypothesis is accumulating, the conditional power should increase as the information fraction increases; however, if the CP does not change as the information fraction increases, it may be unlikely evidence against the null hypothesis is being accumulated. Essentially if CP remains flat across 10%, 20%, 30% of events, it makes it less likely that the null hypothesis would be rejected the null hypothesis at end of study.

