- For each of the conditional power calculation in this analysis, at each cut-off day, subjects with confirmed event or censored on or prior to the cut-off day, time-to-event definition will follow the time to the primary event definition. Subjects with confirmed event after the cut-off day will be censored at the last scheduled or unscheduled visit date prior to the cut-off day. Subjects censored after the cut-off day, time-to-event is censored on the cut-off day.
- Any additional ad hoc analyses requested by the Executive Committee (which will be generated and provided by the CCI Unblinded Statistician).

The above list of additional planned unblinded analyses may be revised by the Executive Committee.

The DSMB will meet, discuss, and decide on a formal recommendation to the Executive Committee regarding continuation of the study with respect to efficacy. Subsequently, the Executive Committee will decide whether or not to stop the trial with respect to efficacy.

In all possible scenarios, the DSMB will clearly document for the Executive Committee whether or not the study appears to be futile, or non-futile, with respect to the conditional power threshold (described below) specified for the primary efficacy analysis.

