9.16.1 Conditional Power for Futility for Efficacy

Any conditional power (CP) is the probability of rejecting a tested null hypothesis at the final analysis, given the interim data and a particular assumption about the population treatment effect. For the futility analysis to be performed in this study after 66 events of MCI due to AD in the high-risk, non-Hispanic/Latino Caucasian study population, rejecting the null hypothesis of no treatment effect with respect to the primary efficacy endpoint at the final analysis is equivalent to the event $\{Z(1) \leq -2.576\}$, and the assumption about the treatment effect is that the population hazard ratio equals the sample hazard ratio observed at the time of this futility analysis. The CP is therefore calculated as

$$CP(t) = \Phi[-(Z(t)/t^{1/2} + 2.576)/(1-t)^{1/2}]$$

where $Z(t)$ is the Wald statistic at information time t computed from the CPH model and Φ is the standard normal cumulative distribution function. If the $CP(t) \leq 30\%$, the study may be deemed futile for demonstrating the superiority of pioglitazone to placebo for the primary efficacy endpoint of time to MCI due to AD at the final analysis after 202 adjudicated events in the high-risk, non-Hispanic/Latino Caucasian study population.

In the above, a z-value of -2.576 corresponds to a one-sided significance level of 0.005; and t will be equal to the number of events in the high-risk, non-Hispanic/Latino Caucasian primary efficacy study population divided by 202.

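### SAP 9.16 gives the DSMB a wrong reading of the conditional-power progression display: under the SAP's own formula, a flat conditional power is an unchanged chance of rejection, not a lower one

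*SAP*

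**What the plan says.** SAP 9.16 adds this display only when CP is above 10% and below 30%. CP is shown at "10% (20 events), 20% (41 events) and 34% (69 events"), with events ordered by time since first dose. The text says that CP should climb as evidence against the null builds up, and that an unchanged CP may mean no such evidence is building up. It concludes: "Essentially if CP remains flat across 10%, 20%, 30% of events, it makes it less likely that the null hypothesis would be rejected". SAP 4.0, item 8, gives the same rationale.

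SAP 9.16.1 defines CP as the probability of rejecting at the final analysis, taking the true HR to equal the one observed at the interim. It also fixes the information time: "t will be equal to the number of events in the high-risk, non-Hispanic/Latino Caucasian primary efficacy study population divided by 202". It places the look at 66 high-risk events. The figure of 69 comes from the opening of SAP 9.16 (and Protocol 13.2), where it is the blinded trigger count that pools high-risk and low-risk subjects.

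For each point of the display SAP 9.16 also sets a censoring rule: "Subjects with confirmed event after the cut-off day will be censored at the last scheduled or unscheduled visit date prior to the cut-off day". Subjects who are censored later are instead censored on the cut-off day itself.

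**The concern.** A CP between 10% and 30% is where the DSMB must use judgement. The 30% threshold has been crossed, but SAP 9.16.1 says only that the study may be deemed futile, and SAP 9.16 makes the result non-binding. The progression is the one listed output reserved for this zone, and it comes with a printed interpretation. If that interpretation is wrong, the DSMB could count against the drug a pattern that says nothing beyond the final CP, or one that a steady benefit would produce. A recommendation to stop cannot easily be undone.

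The fraction and censoring faults matter for a smaller reason: each can move points on the same display without any change in the treatment effect.

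**Working it through.** **Inputs.** Final events 202, two-sided alpha 0.01, power 90% (SAP 8.0, Protocol 13.3). Placebo "will have an event rate of 15% over a 5-year period"; "the target event rate for the active treatment group will be 9% over 5 years"; "1,173 on pioglitazone/1,173 on placebo". Critical value -2.576 and the CP formula (SAP 9.16.1).

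**Reproducing the plan's figures.** With exponential times, HR = ln(0.91)/ln(0.85) = 0.580. Schoenfeld's formula gives 4 × (2.576 + 1.282)² / (ln 0.580)² = 201 events, against 202 stated. The 69 reproduces only as a pooled count. Expected low-risk to high-risk events are 314 × 0.04 / (1,173 × (0.15 + 0.09)) = 12.56/281.5 = 0.0446, and 66 × 1.0446 = 68.9.

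**What a flat CP implies.** The SAP formula is CP(t) = Φ[-(Z/√t + 2.576)/√(1-t)], and it is correct for the stated assumption. Solved for Z: Z = -√t × [2.576 + √(1-t) × Φ⁻¹(CP)]. The matching HR is exp(2Z/√d), where d is the number of events. Holding CP at 20%:

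| High-risk events | t | Z | One-sided p | HR |
|---|---|---|---|---|
| 20 | 0.099 | -0.56 | 0.288 | 0.779 |
| 41 | 0.203 | -0.82 | 0.206 | 0.774 |
| 66 | 0.327 | -1.08 | 0.141 | 0.767 |

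Z nearly doubles while CP does not move, so evidence against the null is accumulating.

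**What a steady observed HR implies.** With Z = ln(HR)√d/2, the formula becomes CP = Φ[(θ - 2.576)/√(1-t)], where θ = -ln(HR)√202/2. CP rises with t only if θ exceeds 2.576, that is, HR below exp(-2 × 2.576/√202) = 0.696. That is the 50% CP line. In the 10% to 30% band a steady HR must give a falling CP:

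| Constant HR | 20 events | 41 events | 66 events |
|---|---|---|---|
| 0.75 | 28.8% | 27.6% | 25.9% |
| 0.767 | 23.3% | 21.9% | 20.0% |
| 0.80 | 14.8% | 13.4% | 11.4% |

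**Does the path add anything to the last CP?** Let B = Z√t. For a true drift -θ, the chance of final rejection given the interim is Φ[(-2.576 - B + θ(1-t))/√(1-t)]. No earlier value appears in it. At CP 20% and 66 events, B = -1.078 × 0.572 = -0.616. True HR 0.70 (θ = 2.535) gives Φ(-0.31) = 38%. True HR 0.58 (θ = 3.871) gives Φ(0.79) = 78%. Simulation agrees (4 million paths per HR, keeping an interim CP of 10% to 30%):

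| True HR | All | CP rose throughout | CP fell throughout |
|---|---|---|---|
| 0.58 | 78% | 78% | 78% |
| 0.70 | 37% | 37% | 37% |
| 0.80 | 13% | 14% | 13% |

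In a separate run of 5 million paths per scenario, restricted to a last CP of 19% to 21%, roughly flat, rising and falling paths rejected in 38.0%, 37.8% and 37.3% (HR 0.70), and in 75.9%, 77.8% and 76.9% (HR 0.58). The flat groups held 1,496 and 872 paths, so their standard errors are about 1.3 and 1.4 points.

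**Event fraction.** 66/202 = 32.7%; 69/202 = 34.2%. For the same Z, using 69 in place of 66 lowers CP from 20.0% to 18.3%, and from 30.0% to 27.8%. The interpretive sentence also says 30% where the display says 34%.

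**Censoring.** Future converters leave the risk set at their last visit before the cut-off; other subjects stay until the cut-off. Time at risk before the cut-off therefore depends on the outcome after it. An illustrative simulation assumed 2,940 subjects, 6-monthly visits, 12% annual dropout, an assumed follow-up distribution and about 69 events in all (51 to 146 trials per HR). The mean CP change was at most 0.7 points and the largest in one trial about 5 points. The effect was greatest at 20 events and near zero at 69.

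**The case against.** Five arguments deserve weight.

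- **The wording is mild, and no decision rule rests on it.** The sentence is comparative. The criterion is CP at or below 30%, the result is non-binding, the Executive Committee decides, and the display sits among Kaplan-Meier curves, repeated-measures, subgroup and joint-model analyses. This stands. A reader might infer that the SAP declares rejection unlikely, or makes a flat CP a reason to stop; the text does neither.
- **A steady HR in this band would fail anyway.** HR 0.767 projects to Z = -1.89 at 202 events, whereas a steady 0.58 gives a rising CP (91%, 93%, 94%). True, but the last CP already says so; the path adds nothing.
- **Read forward from the first point, the sentence holds.** In a simulation starting at CP 15% to 25% with true HR 0.70, flat paths reject in 37% and risen paths in 59%. Risen paths end at a higher CP, which the DSMB has in hand when it reads the display.
- **The path can inform if the effect changes over follow-up.** Events are ordered by time since first dose, and SAP 9.9.3.3 allows for non-proportional hazards. With a 50:50 mix of constant HR 0.75 and delayed HR 0.5 (assuming 2.5-year accrual and 12% dropout), rising against flat paths rejected in 60% and 37% (6-month delay), 44% and 38% (1 year), with no material difference at 2 years. This limits the claim of path-independence to proportional hazards. The SAP does not offer this reason, however, and its CP formula assumes one constant HR.
- **The fraction and censoring faults are small.** Agreed. SAP 9.16.1 should govern t in any case, and later converters really are known to be event-free only at their last prior visit.

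**Conclusion.** The interpretive sentences in SAP 9.16, repeated in SAP 4.0, are wrong under the formula they comment on. A flat CP is an unchanged projected probability of rejection reached with growing evidence, and in the 10% to 30% band a steady observed benefit gives a slightly falling CP, by about 3 points between 20 and 66 events. Given the interim Z, the earlier path is uninformative. This last statement rests on proportional hazards and independent increments, as the SAP's CP does.

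The consequence is a possible lean toward futility in a zone of judgement. A reader might infer a proven bias toward stopping, but guidance that is non-binding and read with other analyses does not establish one. Nor is the 78% rejection rate at HR 0.58 evidence against this display: it concerns the 30% threshold, whichever path led there.

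The pooled count is worth about 2 CP points, and only if 69 were actually used as t for the same Z. The censoring rule is worth less than 1 point on average under the illustrative assumptions. Both should be tidied; neither invalidates the analysis.

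**What to change.** 1. Delete the sentences in SAP 9.16 that interpret a rising or flat CP, and the matching justification in SAP 4.0. Alternatively, replace them with a statement that the display is descriptive, that CP at the last look is the projected probability of rejection, and that under a constant HR the earlier values do not modify it.
2. Set the last display point at the actual number of high-risk events divided by 202, as SAP 9.16.1 defines t, and remove the mismatch between 30% and 34%.
3. At each cut-off, censor every subject without an event by then at the last assessment on or before it, whatever happens later. This matches the censoring principle of SAP 9.9.4.
4. If a delayed effect is the worry, say so and show the HR by follow-up period.

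Optional: report the HR with its confidence interval, and CP under the design HR of about 0.58 beside the current-trend CP. The display itself need not be removed.

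The cost is a short SAP edit, matching wording in the DSMB materials and a small programming change. No new data are needed, and alpha and sample size do not change.

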9.16.1 Conditional Power for Futility for Efficacy

Any conditional power (CP) is the probability of rejecting a tested null hypothesis at the final analysis, given the interim data and a particular assumption about the population treatment effect. For the futility analysis to be performed in this study after 66 events of MCI due to AD in the high-risk, non-Hispanic/Latino Caucasian study population, rejecting the null hypothesis of no treatment effect with respect to the primary efficacy endpoint at the final analysis is equivalent to the event $\{Z(1) \leq -2.576\}$, and the assumption about the treatment effect is that the population hazard ratio equals the sample hazard ratio observed at the time of this futility analysis. The CP is therefore calculated as

$$CP(t) = \Phi[-(Z(t)/t^{1/2} + 2.576)/(1-t)^{1/2}]$$

where $Z(t)$ is the Wald statistic at information time t computed from the CPH model and Φ is the standard normal cumulative distribution function. If the $CP(t) \leq 30\%$, the study may be deemed futile for demonstrating the superiority of pioglitazone to placebo for the primary efficacy endpoint of time to MCI due to AD at the final analysis after 202 adjudicated events in the high-risk, non-Hispanic/Latino Caucasian study population.

In the above, a z-value of -2.576 corresponds to a one-sided significance level of 0.005; and t will be equal to the number of events in the high-risk, non-Hispanic/Latino Caucasian primary efficacy study population divided by 202.

9.17 Changes in the Statistical Analysis Plan from the Protocol Analysis Plan

The study protocol states that academic degrees at baseline will be listed and summarized by treatment group and overall. Information about academic degrees is not collected directly in the eCRF and so won't be presented in the CSR.

Appendix A Criteria for Identification of Markedly Abnormal Laboratory Values
Hematology—Criteria for Markedly Abnormal Values

Parameter	Low Abnormal	High Abnormal
Red blood cells	<0.8 x LLN	>1.2 x ULN
White blood cells	<0.5 x LLN	>1.5 x ULN
Neutrophils	<0.5 x LLN	>1.5 x ULN
Eosinophils	--	>2 x ULN
Basophils	--	>3 x ULN
Lymphocytes	<0.5 x LLN	>1.5 x ULN
Monocytes	--	>2 x ULN
Hemoglobin	<0.8 x LLN	>1.2 x ULN
Hematocrit	<0.8 x LLN	>1.2 x ULN
Platelets (conventional)	<75 x 10 ³ /μL	>600 x 10 ³ /μL
Platelets (SI)	<75 x 10 ⁹ /L	>600 x 10 ⁹ /L
HbA1c (conventional)	--	>7%
HbA1c (SI)	--	>0.07

Chemistry—Criteria for Markedly Abnormal Values

Parameter	Low Abnormal	High Abnormal
ALT	--	>3 x ULN
Alkaline phosphatase	--	>3 x ULN
AST	--	>3 x ULN
Total bilirubin (conventional)	--	>2.0 mg/dL
Total bilirubin (SI)	--	>34.2 µmol/L
Direct bilirubin	--	>2 x ULN
GGT	--	>3 x ULN
Total protein	<0.8 x LLN	>1.2 x ULN
Albumin (conventional)	<2.5 g/dL	--
Albumin (SI)	<25 g/L	--
Creatinine (conventional)	--	>2 mg/dL
Creatinine (SI)	--	>177 µmol/L
Blood urea nitrogen (conventional)	--	>30 mg/dL
Blood urea nitrogen (SI)	--	>10.7 mmol/L
Potassium (conventional)	<3.0 mEq/L	>6.0 mEq/L
Potassium (SI)	<3.0 mmol/L	>6.0 mmol/L
Sodium (conventional)	<130 mEq/L	>150 mEq/L
Sodium (SI)	<130 mmol/L	>150 mmol/L
Glucose (conventional)	<50 mg/dL	>350 mg/dL
Glucose (SI)	<2.8 mmol/L	>19.4 mmol/L
Calcium (conventional)	<7.0 mg/dL	>11.5 mg/dL
Calcium (SI)	<1.75 mmol/L	>2.88 mmol/L
Thyroid Stimulating Hormone (TSH)	<0.8 x LLN	>2.0 x ULN
Vitamin B12 (conventional)	<125 pg/mL	--
Vitamin B12 (SI)	<92 pmol/L	--
Folate (conventional)	<2.2 pg/dL	>17.5 pg/dL
Folate (SI)	<5.0 nmol/L	>39.7 nmol/L
Parathyroid hormone (PTH)	<0.8 x LLN	>2.0 x ULN
Free thyroxine (Free T4)	<0.8 x LLN	>2.0 x ULN
Rapid plasma reagin (RPR)	positive	positive

ALT=alanine aminotransferase, AST=aspartate aminotransferase, GGT=γ-glutamyl transferase, LLN=lower limit of normal, N/A=not applicable, ULN=upper limit of normal.

Urinalysis—Criteria for Markedly Abnormal Values

Parameter	Low Abnormal	High Abnormal
pH	N/A	N/A
Specific Gravity	N/A	N/A
Protein	N/A	N/A
Glucose	N/A	N/A
Blood	N/A	N/A
Nitrite	N/A	N/A

Appendix B Criteria for Abnormal Changes from Baseline of Vital Signs

Vital Sign	Criterion Value	Change Relative to Baseline
Systolic arterial blood pressure	>180 mm Hg	Increase of ≥ 20 mm Hg
	<85 mm Hg	Decrease of ≥ 20 mm Hg
Diastolic arterial blood pressure	>110 mm Hg	Increase of ≥ 15 mm Hg
	<50 mm Hg	Decrease of ≥ 15 mm Hg
Pulse	>120 bpm	
	<50 bpm	
Body Temperature	>37.7 degrees Celsius	
	<35.6 degrees Celsius	
Weight		Change of greater than 7% body weight

Both the criterion value and the change from Baseline must be met.

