10.2.1.3 AESI Reporting

The phase 3 efficacy and safety study will be conducted in cognitively normal elderly subjects. Pioglitazone appears to be safe and well tolerated in the elderly population, based on the available information from healthy volunteers and diabetics in Takeda-sponsored trials or from AD patients in Takeda-supported studies [15,16]. Based on the available safety information in the diabetic population, the following safety procedures will be implemented when specific AESIs are reported during the study. All such AEs will be reported to the Sponsor in an expedited manner irrespective of the event's seriousness or causal relationship:

1. Congestive heart failure (CHF): Subjects and their project partners will be advised to promptly report signs and symptoms of heart failure (eg, excessive, rapid weight gain, dyspnea, and/or edema). Any subject with CHF NYHA class III-IV will be excluded at screening. If a subject develops a new onset CHF or experiences deterioration of pre-existing condition after enrollment, the subject will be withdrawn from the study. Assessment of subjects for signs and symptoms of CHF will take place at every study visit. The diagnosis of CHF can be difficult. Many of the symptoms of heart failure are nondiscriminating and, therefore, of limited diagnostic value. Many of the signs of heart failure result from sodium and water retention and resolve quickly with diuretic therapy, ie, may be absent in patients receiving such treatment. Because the signs and symptoms of heart failure are so non-specific, demonstration of an underlying cardiac cause using diagnostic tests (such as ECG, echocardiogram, chest X-ray, etc) is very important to the diagnosis of heart failure. For

CONFIDENTIAL

events of heart failure, a CHF eCRF should be completed within 24 hours of the investigator's awareness of the event.

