9.14.3 Vital Signs

Vital signs and weight at scheduled visits and their changes from Baseline will be summarized for each treatment group and overall using descriptive statistics by visit and end of study. The number and percentage of subjects with at least one post-Baseline MAV vital sign value during the double-blind treatment period will be presented for each variable over all visits. A listing of MAV vital signs values will also be presented. The criteria for identification of MAV vital signs values are provided in [Appendix B](#).

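### The SAP's weight abnormality criterion has no direction, so its by-arm count adds gains above 7% to losses above 7%

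*SAP*

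**What the plan says.** SAP Appendix B lists the criteria for abnormal vital signs. Systolic pressure has a high row requiring an "Increase of ≥ 20 mm Hg" and a low row requiring a "Decrease of ≥ 20 mm Hg". Diastolic pressure is built the same way. Pulse and temperature each have an upper and a lower limit. Weight has one row: "Change of greater than 7% body weight". A footnote to the whole table adds: "Both the criterion value and the change from Baseline must be met".

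SAP 9.14.3 says how the criteria are used. Counts with percentages are planned: "subjects with at least one post-Baseline MAV vital sign value during the double-blind treatment period will be presented for each variable over all visits". The flagged values are also listed. The same section also gives the conventional output, at each visit and at study end: "Vital signs and weight at scheduled visits and their changes from Baseline will be summarized for each treatment group and overall using descriptive statistics".

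On the clinical side, Protocol 10.2.1.3 asks subjects and partners to report signs of heart failure promptly and gives as examples "excessive, rapid weight gain, dyspnea, and/or edema". Protocol 4.1 lists heart failure and peripheral edema from dose-related fluid retention among the known risks, at doses well above the one studied here. Protocol 9.1.4 schedules weight at baseline, every 6 months and at the final visit.

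**The concern.** The count of subjects with an abnormal value is the only planned table that says how many subjects in each arm crossed a weight threshold. As written, it cannot say which way they crossed it. The documents' stated worry for this drug is gain. Loss above 7% for any reason enters the same numerator and, if it occurs at a similar rate in both arms, pulls the arm ratio toward 1. If loss is less frequent on drug, it offsets an excess of gain directly. A reader of the study report would then see similar percentages in the two arms and could not tell whether gain was balanced.

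The footnote adds a smaller problem. It demands both a criterion value and a change from baseline, but the weight row has no criterion value, and pulse and temperature have no change criterion. Taken literally, none of those three can ever be flagged.

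**Working it through.** The documents attach no rate, power or sample size to this criterion, so there is no planned figure to reproduce. The check has a textual part and an illustration.

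**Text.** Rows of Appendix B side by side:

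| Vital sign | High side | Low side | Change criterion |
|---|---|---|---|
| Systolic pressure | >180 mm Hg | <85 mm Hg | directional, 20 mm Hg |
| Diastolic pressure | >110 mm Hg | <50 mm Hg | directional, 15 mm Hg |
| Pulse | >120 bpm | <50 bpm | none |
| Temperature | >37.7 °C | <35.6 °C | none |
| Weight | none | none | >7%, no direction |

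Weight is the only row without a high and a low side. Section 9.14.3 does not restore direction, so the flagged count is subjects with any gain above 7% plus subjects with any loss above 7%, with a subject who had both counted once.

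**Illustration of dilution.** Inputs:
- 1,470 subjects per high-risk arm (Protocol 6.1, the enrolment estimate after Amendment 5).
- Gain above 7%: assumed 4% on placebo and 6% on drug.
- Loss above 7%: assumed 0% to 20%, the same in both arms.
- No subject has both.

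Ratio for the pooled row = (gain on drug + loss) / (gain on placebo + loss). Power is for a two-sided 5% comparison of two proportions: Φ[(d − 1.96·SE0)/SE1], where d is the difference, SE0 = √(2·p̄(1−p̄)/1,470), p̄ is the average of the two proportions, and SE1 = √((p1(1−p1)+p2(1−p2))/1,470).

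| Loss in both arms | Placebo vs drug | Ratio | Power |
|---|---|---|---|
| 0% (gain-only row) | 4% vs 6% | 1.50 | 70% |
| 5% | 9% vs 11% | 1.22 | 44% |
| 10% | 14% vs 16% | 1.14 | 33% |
| 20% | 24% vs 26% | 1.08 | 24% |

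With gain at 5% vs 8%, the gain-only row has ratio 1.60 and power 91%. With 10% loss in both arms it becomes 15% vs 18%, ratio 1.20, power 59%.

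**Illustration of cancellation.** Gain 4% vs 6% and loss 10% vs 8%: the pooled row is 4+10 = 14% on placebo and 6+8 = 14% on drug, ratio 1.00.

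**Does the signed mean change hide the same thing?** Take the cancellation case and assume, for one time point, that percentage change is normal in each arm. Then SD = 14/(z_gain + z_loss) and mean = 7 − z_gain·SD, where each z cuts off the stated tail.
- Placebo: z = 1.751 and 1.282, SD = 14/3.032 = 4.62, mean = −1.08.
- Drug: z = 1.555 and 1.405, SD = 14/2.960 = 4.73, mean = −0.35.
- Difference 0.73; standard error √((4.62² + 4.73²)/1,470) = 0.172; z = 4.2.

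So the pooled count shows nothing while the signed mean shows a clear shift. The two summaries do not fail together.

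**The case against.** The strongest reply is that little is lost. Change from baseline is signed and is summarized by visit and arm with mean, SD or SE, median, minimum and maximum (SAP 9.1.2 and 9.14.3). More gain and less loss both push it upward, as the last calculation shows. Heart failure is an adverse event of special interest with its own summary and case report form. Edema or weight-increase events reported as adverse events appear in the by-arm tables. Flagged values are listed, so direction can be recovered subject by subject. The weight row is also descriptive and no test is planned on it, so the power figures are only a yardstick. All of this stands, and it limits the point to one table. What it does not supply is a by-arm count of subjects who gained more than 7%: neither summary statistics nor a subject listing gives that. Weight has no shift table either, unlike the laboratory parameters and the ECG interpretation.

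A reader might go further and infer that the trial would miss its clearest fluid-retention signal. The documents do not support that. The protocol's warning sign is rapid gain, whereas this flag is a change from baseline measured every 6 months over years, so even a gain-only row would mix fluid with ordinary weight gain. The fluid-retention risk is also described at 15-45 mg, not at 0.8 mg.

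A reader might also put the diluting losses down to ageing or dementia and call them common. Neither document says so. Subjects enter cognitively normal, and confirmed Alzheimer's dementia leads to withdrawal (Protocol 6.2.4).

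**Conclusion.** The point holds as a minor defect of presentation. Followed as written, the SAP's by-arm weight abnormality count cannot separate gain from loss, although gain is the direction of concern in the protocol. Dilution follows whenever some subjects lose more than 7%; its size is unknown, because neither document gives rates of gain or loss. On assumed rates, a gain ratio of 1.50 becomes 1.22 to 1.08 with 5-20% background loss in both arms, and can vanish if loss is less frequent on drug. The arm size of 1,470 is likewise an estimate of enrolment, not the number with weights at any visit. The defect touches no endpoint, error rate, sample size or stopping rule, and direction survives in the signed changes and the listings. A gain-only row would be supportive evidence on fluid retention alongside the heart-failure and adverse event summaries.

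**What to change.** In SAP Appendix B, replace the single weight row with two: increase of more than 7% from baseline, and decrease of more than 7% from baseline. In 9.14.3, state that each is tabulated by arm over all visits with the same denominator, and that a subject who meets both is counted in each. Keep the signed-change summary as it is. In the same edit, restrict the footnote requiring both a criterion value and a change to the blood pressure rows.

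The cost is one extra table row and a reworded footnote. The weights are already collected, and nothing changes for sites or subjects.
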